3.3.2 Exclusion Criteria

1. Target Disease Exceptions

- a) Any history of atrial fibrillation (AF) other than transient AF related to cardiac surgery
- b) Severe left ventricular systolic dysfunction, left ventricular thrombus, or other high-risk cardioembolic source deemed the likely cause of brain ischemia
- c) TIA symptoms limited to isolated numbness, isolated visual changes, or isolated dizziness/vertigo
- d) Carotid or vertebral stenosis for which there is a plan for revascularization therapy
- e) Any condition requiring ongoing treatment with an anticoagulant after discharge. For prophylactic measures to prevent deep vein thrombosis (DVT), pneumatic pressure devices are preferred

2. Medical History and Concurrent Diseases

- a) Subjects with known bleeding diathesis or coagulation disorder (eg, thrombotic thrombocytopenic purpura)
- b) History of previous non-traumatic or traumatic intracranial hemorrhage at any time
- c) Acute gastrointestinal ulcer or history of gastrointestinal (GI) bleed which required medical treatment within the past 3 months

- d) Planned or anticipated invasive surgery or procedure during study duration
- e) Persistent, uncontrolled hypertension (systolic BP > 180 mm Hg, or diastolic BP > 100 mm Hg) that does not respond to acute treatment
- f) Moderate or severe hepatic impairment, defined as Child-Pugh Class B or C; (see [Appendix 5](#))
- g) Moderate to severe renal impairment, defined as estimated glomerular filtration rate (eGFR) < 45 mL/min; (see [Section 5.3.7.1](#))
- h) Any other reason, in the opinion of the investigator that the subject may be at undue risk from study participation
- i) Qualifying ischemic event induced by angiography or surgery
- j) Any gastrointestinal surgery that could impact upon the absorption of study drug
- k) Inability to tolerate oral medication or swallow tablets whole
- l) Inability to undergo venipuncture and/or tolerate venous access
- m) Subjects in whom MRI procedures cannot be performed. [Section 3.4.3](#) provides a list of some common conditions that may preclude the subjects from having MRI. However, this should not be used as a substitute for local clinical standards of care. The ultimate decision to perform any of these procedures in an individual subject in this study rests with the site radiologist, the investigator and the standard set by the local ethics committee/institutional review board
- n) Any other medical, psychiatric and/or social reason including drug or alcohol abuse which in the opinion of the investigator may impact the subject's ability to comply with study procedures
- o) Subjects who have received intravenous or intra-arterial thrombolysis or mechanical thrombectomy within the past 48 hours or who are currently eligible and able to receive these treatments for their current stroke

3. Physical and Laboratory Test Findings

- a) Any of the following on 12-lead electrocardiogram (ECG) prior to study drug administration, confirmed by repeat
 - i) Atrial fibrillation or atrial flutter
 - ii) Complete heart block or Mobitz 2 second degree heart block
 - iii) QRS \geq 180 msec
 - iv) QT \geq 500 msec
 - v) QTcF \geq 450 msec (Not applicable per Protocol Amendment 06)
- b) Platelet count < $100 \times 10^3/\mu\text{L}$ ($100 \times 10^9/\text{L}$)
- c) Hemoglobin (Hb) < 9 g/dL

4. Allergies and Adverse Drug Reaction

- a) History of allergy to BMS-986141, acetylsalicylic acid, or related compounds

- b) History of any significant drug allergy (such as anaphylaxis or hepatotoxicity)
- c) History of drug-induced hematologic or hepatic abnormalities

5. Other Exclusion Criteria

- a) Prisoners or subjects who are involuntarily incarcerated. (Note: under certain specific circumstances a person who has been imprisoned may be included or permitted to continue as a subject. Strict conditions apply and Bristol-Myers Squibb approval is required.)
- b) Subjects who are compulsorily detained for treatment of either a psychiatric or physical (eg, infectious disease) illness

6. Prohibited Medications

- a) Any investigational drug or placebo exposure within 4 weeks of study drug administration is prohibited
- b) Any prior exposure to BMS-986141
- c) Planned use of anticoagulants including warfarin or other vitamin K antagonists, oral thrombin and factor Xa inhibitors, bivalirudin, hirudin, argatroban, unfractionated and low molecular weight heparins, with the exception of heparin or low molecular weight heparin (LMWH) used to maintain patency of indwelling catheters or for prophylaxis of venous thromboembolism (VTE)
- d) Planned use of antiplatelet therapy other than study medication or ASA at a dose from 75 to 162 mg. including ASA at a dose < 75 mg/day or > 162mg/day, GPIIb/IIIa inhibitors, clopidogrel, ticlopidine, prasugrel, dipyridamole, ozagrel, cilostazol, and ticagrelor. Treatment with ASA at a dose >162 mg/day before randomization is allowed.
- e) Receipt of any intravenous or intra-arterial thrombolysis within 48 hours of randomization (This criterion is Not Applicable per Protocol Amendment 06; refer to Exclusion Criteria 2o)
- f) Anticipated requirement for ongoing treatment with non-steroidal anti-inflammatory drugs (NSAIDs). COX-2 inhibitors are allowed. NSAID use prior to randomization is allowed
- g) Use of strong CYP3A4 inhibitors or strong CYP3A4 inducers in the 7 days prior to randomization or the need for ongoing treatment with concomitant oral or intravenous therapy with strong CYP3A4 inhibitors or strong CYP3A4 inducers during the study.

Eligibility criteria for this study have been carefully considered to ensure the safety of the study subjects and that the results of the study can be used. It is imperative that subjects fully meet all eligibility criteria.

3.4 Concomitant Treatments

3.4.1 Prohibited and/or Restricted Treatments

Any investigational drug or placebo exposure during and 60 days post study drug administration is prohibited.

Use of the following treatments is prohibited during the treatment period:

- Anticoagulants including warfarin or other vitamin K antagonists, oral thrombin and factor Xa inhibitors, bivalirudin, hirudin, argatroban, unfractionated and LMWH, with the exception of heparin or LMWH used to maintain patency of indwelling catheters or for prophylaxis of VTE
- Antiplatelet therapy other than study medication or ASA at a dose from 75 to 162 mg/day including ASA at a dose < 75 mg/day or > 162 mg/day, GPIIb/IIIa inhibitors, clopidogrel, ticlopidine, prasugrel, dipyridamole, ozagrel, cilostazol, and ticagrelor
- Requirement for treatment with concomitant oral or intravenous therapy with strong CYP3A inhibitors or CYP3A4 inducers
- Ongoing treatment with non-steroidal anti-inflammatory drugs (NSAIDs); COX-2 inhibitors are allowed

For WOCBP the use of hormonal contraceptives should not be the primary method of contraception; women may continue on these medications but must commit to using another method of highly effective birth control while on study. See [Section 3.3.1](#).

The following medical procedures are prohibited while the subject is receiving study medication: carotid revascularization such as endarterectomies and stenting.

If treatment with the therapies noted above, except for strong CYP3A4 inhibitors or strong CYP3A4 inducers, becomes necessary, the study medication should be stopped temporarily up to a maximum of 14 days while subjects are treated with the prohibited medications. Study medication should be restarted upon completion of treatment with the prohibited therapy. Subjects who will require treatment with strong CYP3A4 inhibitors or strong CYP3A4 inducers must be discontinued from study treatment. It is recommended the strong CYP3A4 inhibitor or inducer is not started until at least 24 hours after the last dose of study medication. For guidance related to dosing of study medication, please refer to [Section 4.5](#).

3.4.2 Other Restrictions and Precautions

The potential for drug interactions between BMS-986141 and statins (eg, atorvastatin, rosuvastatin, simvastatin) has not been evaluated in a clinical study and may occur when they are taken at the same time. Statins should be dosed at least 4-6 hours after administration of BMS-986141.

It is strongly recommended that subjects refrain from drinking grapefruit juice throughout the duration of the treatment period of the study.

3.4.3 MRI Contraindications

- 1) Subjects who have a history of claustrophobia.
- 2) Subjects who have a physical limitation related to fitting in the bore of the magnet (ie, weight greater than that allowable by the MRI table).

- 3) Subjects with a pacemaker, epicardial pacemaker wires, MRI-incompatible cardiac valve prostheses, and MRI-incompatible vascular clips less than two-months old, or MRI-incompatible aneurysm clips of any age.
- 4) Subjects with MRI-incompatible cochlear implants.
- 5) Subjects with spinal nerve stimulators.
- 6) Subjects with an infusion pump.
- 7) Subjects with tattoos near the eye.
- 8) Subjects with metallic fragments in the eyes/orbits or in the vicinity of the brain or major neurovascular structures of the body.
- 9) Subjects with an employment history, which involves exposure to welding; unless absence of metallic fragments is documented by X-ray examination as per institutional practice.
- 10) Subjects who have shrapnel at any place in their body.

3.5 Discontinuation of Subjects following any Treatment with Study Drug

During treatment period circumstances may arise which require temporary or permanent discontinuation of investigational product. For guidance related to the temporary discontinuation please refer to [Section 3.4.1](#).

Subjects MUST discontinue investigational product (and non-investigational product at the discretion of the investigator) for any of the following reasons:

- Subject's request to stop study treatment
- Any clinical adverse event (AE), laboratory abnormality or intercurrent illness which, in the opinion of the investigator, indicates that continued participation in the study is not in the best interest of the subject
- Any clinical condition requiring treatment with a prohibited medication for more than 14 days
- Termination of the study by Bristol-Myers Squibb (BMS)
- Loss of ability to freely provide consent through imprisonment or involuntarily incarceration for treatment of either a psychiatric or physical (eg, infectious disease) illness
- Severe non-compliance to protocol, as judged by the investigator and/or Sponsor (BMS)
- Incorrect enrollment (ie, the subject does not meet the required inclusion/exclusion criteria) for the study, as determined after consultation with the sponsor
- Pregnancy
- Moderate or severe renal impairment defined as eGFR < 45 mL/min (see [section 5.3.7.1](#)) for more than 7 days.
- Subjects with an ALT and/or AST > 3× ULN will be scheduled for a follow up visit within 3 days following the receipt of the result. Subjects should be discontinued from study if the initial and repeat laboratory tests meet any of the following criteria:
 - ◆ ALT and/or AST are > 3× ULN and total bilirubin (TB) > 2× ULN

- ◆ ALT and/or AST are $> 5 \times$ ULN for ≥ 14 consecutive days, at any time after initial confirmatory results
- ◆ ALT and/or AST are $\geq 10 \times$ ULN
- Subjects requiring treatment with strong CYP3A4 inhibitors or strong CYP3A4 inducers
- Subjects treated with any intravenous or intra-arterial thrombolysis or with mechanical thrombectomy

In the case of pregnancy, the investigator must immediately notify the Sponsor or designee of this event. In most cases, the study drug will be permanently discontinued in an appropriate manner (eg, dose tapering if necessary for subject safety). Please contact the Sponsor or designee within 24 hours of awareness of the pregnancy. If the investigator determines a possible favorable benefit/risk ratio that warrants continuation of study drug, a discussion between the investigator and the Sponsor or designee must occur.

All subjects who discontinue study drug should comply with protocol specified follow-up procedures as outlined in [Section 5](#). The only exception to this requirement is when a subject withdraws consent for all study procedures including post-treatment study follow-up or loses the ability to consent freely (ie, is imprisoned or involuntarily incarcerated for the treatment of either a psychiatric or physical illness).

If study drug is discontinued prior to the subject's completion of the study, the reason for the discontinuation must be documented in the subject's medical records and entered on the appropriate case report form (CRF) page.

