A study visit will be performed on the day of hospital discharge. Subjects will be instructed to report any adverse events occurring after hospital discharge, including any occurrence of bleeding or signs or symptoms of recurrent stroke.

The study site will contact the subject by telephone on Day 10 \pm 3 days to assess study medication compliance and assess the subject's health status.

A study visit will be performed 28 \pm 3 days after the first dose of study medication. Head MRI will be performed for assessment of unrecognized brain infarctions. For subjects enrolled in Part 1 of the study, Day 28 will be the end of the treatment period and it is preferred that the study visit be performed on Day 28 or earlier.

Part 2 of the study will only be initiated after regulatory review of 90-day preclinical toxicology study reports and the updated Investigator Brochure. For subjects enrolled in Part 2 of the study, the treatment period will be 90 days. There will be no change in study visits through Day 28. Additional treatment period study visits for these subjects will occur 56 and 90 days after the beginning of the treatment period.

Pharmacokinetic (PK) sampling will be performed in all subjects. See [Section 5.5](#).

A sub-study conducted at select sites will enroll approximately 50 subjects per arm for which additional blood will be collected for analysis of platelet aggregation as a pharmacodynamic biomarker. See [Section 5.6](#).

Follow-Up Period

The follow-up period will last until the later of 90 days after the first dose of study drug or 30 days after treatment discontinuation. Subjects will be instructed to report any adverse events that occur during the follow-up period. No additional study assessments are planned at the follow-up visit, which may be an in-person study visit or if necessary conducted by telephone.

Duration of Study

The expected duration of the study, from first subject, first visit through the last subject, last follow-up visit (eg, the End of the study), is approximately 28 months.

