3.6 Post Study Drug Study Follow up

In this study, major adverse cardiovascular events (MACE) and the Day 28 MRI is a key endpoint of the study. Post treatment follow-up is of critical importance and is essential to preserving subject safety and the integrity of the study. Subjects who discontinue study drug must continue to be followed for collection of outcome and/or survival follow-up data as required and in line with Section 5 until death or the conclusion of the study.

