3.6.1 Withdrawal of Consent

Subjects who request to discontinue study drug will remain in the study and must continue to be followed for protocol specified follow-up procedures. The only exception to this is when a subject specifically withdraws consent for any further contact with him/her or persons previously authorized by subject to provide this information. Subjects should notify the investigator of the decision to withdraw consent from future follow-up **in writing**, whenever possible. The withdrawal of consent should be explained in detail in the medical records by the investigator, as to whether the withdrawal is from further treatment with study drug only or also from study procedures and/or post treatment study follow-up, and entered on the appropriate CRF page. In the event that vital status (whether the subject is alive or dead) is being measured, publicly available information should be used to determine vital status only as appropriately directed in accordance with local law.

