6.1.1 Serious Adverse Event Collection and Reporting

Sections 5.6.1 and 5.6.2 in the Investigator Brochure (IB) represent the Reference Safety Information to determine expectedness of serious adverse events for expedited reporting. Following the subject's written consent to participate in the study, all SAEs, whether related or not related to study drug, must be collected, including those thought to be associated with

protocol-specified procedures. All SAEs must be collected that occur during the screening period and within 30 days of discontinuation of dosing or subject's participation in the study, if the last scheduled visit occurs at a later time. If applicable, SAEs must be collected that relate to any later protocol specified procedure.

The investigator must report any SAE that occurs after these time periods and that is believed to be related to study drug or protocol-specified procedure.

An SAE report must be completed for any event where doubt exists regarding its seriousness.

If the investigator believes that an SAE is not related to study drug, but is potentially related to the conditions of the study (such as withdrawal of previous therapy or a complication of a study procedure), the relationship must be specified in the narrative section of the SAE Report Form.

SAEs, whether related or not related to study drug, and pregnancies must be reported to Sponsor (or designee) within 24 hours of awareness of the event. SAEs must be recorded on the SAE Report Form; pregnancies on a Pregnancy Surveillance Form (electronic or paper forms). The preferred method for SAE data reporting collection is through the eCRF. The paper SAE/pregnancy surveillance forms are only intended as a back-up option when the eCRF system is not functioning. In this case, the paper forms are to be transmitted via email or confirmed facsimile (fax) transmission to:

SAE Email Address: Refer to Contact Information list.

SAE Facsimile Number: Refer to Contact Information list.

For studies capturing SAEs through electronic data capture (EDC), electronic submission is the required method for reporting. In the event the electronic system is unavailable for transmission, paper forms must be used and submitted immediately. When paper forms are used, the original paper forms are to remain on site.

SAE Telephone Contact (required for SAE and pregnancy reporting): Refer to Contact Information list.

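### The ALT/AST rule in Protocol 3.5 takes subjects out of the study, where the rest of the protocol stops study drug only (minor wording error)

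*Protocol*

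**What the plan says.** The list in Protocol 3.5 opens: "Subjects MUST discontinue investigational product (and non-investigational product at the discretion of the investigator) for any of the following reasons". One item covers ALT or AST above three times the upper limit of normal. It calls for a follow-up visit within 3 days of receiving the result, and then states: "Subjects should be discontinued from study if the initial and repeat laboratory tests meet any of the following criteria". Three criteria follow:

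- ALT/AST above 3 times the limit, with total bilirubin above 2 times;
- ALT/AST above 5 times for at least 14 consecutive days;
- ALT/AST at or above 10 times.

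The closing text of Section 3.5 tells everyone who stops study drug to comply with the follow-up procedures, and then limits the exemptions: "The only exception to this requirement is when a subject withdraws consent for all study procedures including post-treatment study follow-up". The same sentence adds loss of the ability to consent freely. Liver criteria are not mentioned.

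Section 3.6 says "Subjects who discontinue study drug must continue to be followed for collection of outcome and/or survival follow-up data", until death or the conclusion of the study. Section 3.6.1 says "Subjects who request to discontinue study drug will remain in the study and must continue to be followed". In Section 3.1, "The follow-up period will last until the later of 90 days after the first dose of study drug" or 30 days after treatment discontinuation.

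**The concern.** The protocol treats stopping drug and leaving the study as different things. Section 3.6.1 requires the investigator to record which of the two a withdrawal means. An instruction to discontinue someone *from study* therefore has a definite meaning here, and it is the wrong one for this item.

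A site would consult this bullet at the moment a liver signal appears. If it acted on the words as written, follow-up would end because of a laboratory finding that the drug may have caused. Loss of that kind could differ between arms, and it would fall on subjects whose later course is of particular interest.

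**Working it through.** There is no stated figure to reproduce. The check sets the relevant places side by side, then traces what a literal reading would remove and what would remain.

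**1. Which reading the protocol supports**

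- *Section 3.5, opening line.* It governs every item in the list and stops investigational product.
- *Section 3.5, neighbouring items.* Two others mention the study: continued participation not in the subject's interest, and termination by the sponsor. Both give reasons to stop drug, and neither orders removal of a subject. The ALT/AST item is the outlier.
- *Section 3.4.1.* For strong CYP3A4 inhibitors and inducers, which are on the same list, the wording is consistent with drug-only stopping: "Subjects who will require treatment with strong CYP3A4 inhibitors or strong CYP3A4 inducers must be discontinued from study treatment".
- *Section 3.5, closing text.* There are two exemptions from follow-up, and neither is a laboratory criterion.
- *Sections 3.6 and 3.6.1.* Follow-up continues after drug is stopped.
- *Tables 5.1-2 and 5.1-3.* Footnote a keeps subjects in all visits after dosing stops. The MRI note keeps the Day 28 scan for those who stop early.

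Every other place points to drug only.

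**2. What a literal reading would remove**

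Chemistry is drawn on Day 1, at hospital discharge and on Day 28, and in Part 2 also on Days 56 and 90. The rule needs an initial and a repeat test, so action comes some days after the first abnormal sample.

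- *Confirmed before Day 28, either part.* The Day 28 visit and MRI are lost, with everything after them. Under SAP 4.1, a subject with no MRI result and no counted symptomatic ischemic stroke has a missing primary endpoint.
- *Part 1, Day 28 sample.* Section 4.5 already ends dosing on Day 28, so no drug is left to stop. A literal reader could still cancel the Day 90 contact. This is the weakest application of the bullet.
- *Part 2, Day 28 sample.* The Day 56, 90 and 120 visits are lost. From the Day 56 sample, the Day 90 and 120 visits are lost.

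Wherever the Day 90 contact is lost, MACE by Day 90 is incompletely observed. MACE is the only secondary endpoint in the sequential testing (Protocol 8.4.2.2, SAP 7.5.2).

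**3. What would continue anyway**

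- *Section 6.1.1:* "All SAEs must be collected that occur during the screening period and within 30 days of discontinuation of dosing". After the required collection period, SAEs believed related to study drug or a protocol procedure must still be reported.
- *Sections 6.1.1 and 6.6.* A case meeting the potential drug-induced liver injury definition is reported as an SAE and followed to resolution or stabilization.
- *Sections 6.2.1 and 6.3.* A laboratory abnormality that requires study drug to be stopped is recorded as an adverse event, and follow-up is required for a nonserious event that causes discontinuation. This covers cases that fall outside the liver-injury definition.

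What is exposed is therefore the scheduled visits, the MRI and complete endpoint ascertainment. Follow-up of the liver event itself is not exposed.

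**4. Effect on the planned figures**

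Correcting the words changes none of them: 1312 randomized, 1240 evaluable, at least 80% power at one-sided 15%.

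**The case against.** The strongest reply is that the protocol already settles the matter. The bullet sits under a line that stops product only, the same section closes with an exhaustive exemption, and Section 3.6 and both schedules repeat the rule. Harm requires a site to follow two words and disregard all of that. This is largely right. It is why the point is graded minor and why drug-only stopping is taken as the intent. It does not remove the contradiction, because the bullet is a direct instruction and a site handling a liver signal may read it alone.

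The second reply is that the harm is easily overstated. That is also right. A reader might infer that safety observation ends when the bullet is applied. Sections 6.1.1, 6.2.1, 6.3 and 6.6 do not support that, as shown in the working.

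A reader might also infer that the trial is designed to drop subjects with liver signals, or that the primary analysis is at risk. The documents do not support either inference. The design plainly keeps these subjects, and nothing suggests that enough of them would meet confirmed criteria to matter for power. Counts of days lost or changes in power would rest on an event rate that the documents do not give, so none is offered.

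**Conclusion.** The point holds as a minor internal contradiction. One item in Protocol 3.5 orders removal from the study, where its own list and every related section stop investigational product only. The finding concerns the wording of an operative instruction and is not a design flaw.

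Its practical size depends on two unknowns: how many subjects meet the confirmed criteria, and how many sites would read the item literally. The documents give neither. On the assumption that both are small, the effect on power is negligible. What remains is avoidable loss of visits, Day 90 MACE ascertainment and occasionally the primary endpoint in individual subjects, for a reason that could be related to treatment.

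**What to change.** In the ALT/AST item of Protocol 3.5, replace *discontinued from study* with *discontinued from investigational product*, and add a reference to Sections 3.6 and 5 for continued follow-up. Leave the three laboratory criteria and the repeat-test requirement unchanged.

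The cost is a few words in the next amendment or an administrative letter. The study has already used a letter to correct the unit in the hemoglobin exclusion criterion. No visit, procedure, sample size or analysis changes.
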